### **5.10.3 Summary of adverse pregnancy outcomes**

Note: The evaluations of small for gestational age, premature birth, low birth weight and congenital anomalies are based on live births. Multiple births with both live birth and stillbirth outcomes will be counted as pregnancies with stillbirths and other adverse pregnancy outcomes that may have been observed. Pregnancy outcome of induced abortion will be excluded from adverse pregnancy outcome summaries.

- Table with number (%) of pregnancies resulting in each of the following adverse pregnancy outcomes:
  - Fetal demise (stillbirth, spontaneous abortion)
  - Premature birth (<37 weeks gestation)
  - Low birth weight (<2,500 grams)
  - Congenital anomalies
  - Any adverse pregnancy outcome excluding congenital anomalies (defined as any of the above excluding congenital anomalies)
  - Any adverse pregnancy outcome (defined as any of the above)
- Table with number (%) of pregnancies resulting in each of the following severe adverse pregnancy outcomes:
  - Fetal demise (stillbirth, spontaneous abortion)
  - Premature birth (<34 weeks gestation)
  - Low birth weight (<1,500 grams)
  - Any severe adverse pregnancy outcome (defined as any of the above)

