## **Introduction**

### **1.1 Purpose of the Statistical Analysis Plan (SAP)**

This statistical analysis plan has been developed to (1) provide a structured time-frame for database completion and preparation of the final primary analysis report; (2) facilitate discussion of the key statistical analysis components amongst the study team; (3) provide agreement between the study team and statisticians regarding the statistical analyses to be performed; and (4) aid in setting priorities relating to the data cleaning and development of statistical analysis programs.

The statistical analysis plan contains details of all statistical analyses that will be completed for the final primary analysis report.

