## **2 Study Objectives (Protocol Version 2.0)**

The primary analysis report will include the primary objective and secondary objectives 1-4 (listed in sections 2.1 and 2.2 below). Secondary objectives 5-7 and the exploratory objectives (section 2.3) will be addressed in separate analysis plans.

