### **2.2 Secondary Objectives**

1. To compare safety and toxicity of INH *in utero* exposure and on infants on study
2. To compare TB incidence and all-cause mortality in HIV-infected women and their infants enrolled on study
3. To compare overall safety and hepatotoxicity, as well as evaluate risk factors for these outcomes, during pregnancy and immediate postpartum in women on immediate versus deferred INH therapy
4. To evaluate for INH resistance among *M.tb.* isolates from HIV-infected women and infants who develop TB while on study
5. To evaluate the intensive pharmacokinetics of INH and selected ARV drugs in a subset of HIV-infected pregnant and postpartum women receiving HAART
6. To evaluate and compare the performance characteristics of IGRA (TB ELISPOT and QGIT) with TST in HIV-infected women and their infants
7. To compare adherence in women initiating immediate versus deferred INH preventive therapy via self-report and pill counts

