### **3.2 Secondary Endpoints**

- ***In utero* exposure and infant endpoints:**
  - Fetal death
  - Small for gestational age
  - Premature birth (< 37 weeks gestation)
  - Low birth weight (< 2500 gm)
  - Congenital anomalies
  - Grade 3 or higher clinical or laboratory AEs
    - ◆ all AEs
    - ◆ possibly, probably, or definitely related to INH/Placebo for INH
  - HIV infection
  - Hospitalization
- **Any of the following endpoints:**
  - Maternal TB (probable or confirmed – see Appendix 100 for definitions)
  - Infant TB (probable or confirmed, as defined in Appendix 100, and congenital TB, as defined using the Cantwell criteria)
  - Death of infant
  - Death of mother
  - Combined endpoint of maternal TB or maternal death
  - Combined endpoint of infant TB or infant death
  - Combined endpoint of maternal TB, maternal death, infant TB, or infant death

NOTE: TB endpoints and infant cause of death will be reviewed by a Secondary Endpoint Review Committee (SERC), which consists of maternal and pediatric TB specialists who may be

members of the study team. Refer to the Endpoint Review Process document for details of the review process. Appendix 100 will be the basis for adjudication of the TB endpoint by the SERC and is available in the CRF Appendix Codes section of the Frontier Science IMPAACT Portal; the web link to portal can be found in the MOP. Cantwell criteria for Congenital TB are in the MOP and will be collected on the P1078 CRF.

Deaths of enrolled women will receive external review by the IERC for adjudication of study treatment attribution and will also be reviewed by the SERC. The SERC will consider if the cause of death (COD) is due to unrecognized active TB (expected to be rare), from a known cause other than active TB, or from an unknown cause.

- **Occurrence of each of the following safety outcomes in HIV-infected women: during pregnancy up to: (i) delivery (antenpartum) and (ii) 12 weeks postpartum**
  - Grade  $\geq$  3 AEs possibly, probably, or definitely related to INH/Placebo for INH or permanent discontinuation of INH/Placebo for INH due to an adverse event
  - Grade  $\geq$  3 AEs (all-cause)
  - Hepatotoxicity possibly, probably, or definitely related to INH/Placebo for INH
  - Hepatotoxicity (all-cause)

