## 5.10 *In Utero* Exposure and Infant Outcomes

Validation: The analysis programs in this section will be validated, but not double-programmed.

Note: Exact categorical tests (with mid-p adjustment for the case of Fisher's exact tests) will be employed to compare the difference in outcomes between arms.

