### 5.10.2 Infant baseline characteristics

- Gender: number (%) by category [EVW0292]
- Gestational age at birth (weeks): N, N missing, min, max, median (Q1-Q3); number (%) by category (<34, 34 -<37,  $\geq 37$ )
  - Note: The calculation of gestational age at birth will be based on three sources, prioritized as follows: newborn exam [PE5896], pregnancy outcome evaluation [EVW0292] and mother's gestational age at enrollment [OBW0006] plus number of weeks to delivery.
- Birth weight (grams): N, N missing, min, max, median (Q1-Q3); number (%) by category (<1500, 1500 -<2500,  $\geq 2500$ ) [PE5896]

- Apgar score at 1 minute: N, N missing, min, max, median (Q1-Q3); number (%) by category (0-3, 4-6, 7-10) [PE5896]

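### Small for gestational age is a declared secondary endpoint with a stated live-birth basis, but no output in SAP section 5 reports it

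*SAP*

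**What the plan says.** Section 3.2 lists eight in utero and infant endpoints; the second is "Small for gestational age". They serve secondary objective 1 in section 2.2, which compares the safety and toxicity of INH through in utero "exposure and on infants on study".

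Section 5.10.3 opens with a note on the analysis basis: "The evaluations of small for gestational age, premature birth, low birth weight and congenital anomalies are based on live births". Two tables follow. The first gives the number and percentage "of pregnancies resulting in each of the following adverse pregnancy outcomes": fetal demise, premature birth before 37 weeks, low birth weight under 2,500 g, congenital anomalies, and two composites, one leaving out congenital anomalies and one including them. The second, for severe outcomes, has fetal demise, premature birth before 34 weeks, low birth weight under 1,500 g, and a composite. Each composite is defined by the rows listed above it.

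For everything in section 5.10, exact categorical tests, with a mid-p adjustment for Fisher's test, "will be employed to compare the difference in outcomes between arms".

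On scope, section 1.1 states: "The statistical analysis plan contains details of all statistical analyses that will be completed for the final primary analysis report". Section 2 adds: "The primary analysis report will include the primary objective and secondary objectives 1-4". Only secondary objectives 5-7 and the exploratory objectives are left to separate plans.

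**The concern.** The note sets a denominator for an SGA evaluation that the tables beneath it never produce. Of the four outcomes it names, three have a row and SGA does not. That looks like an oversight, since an author who meant to drop the endpoint would hardly have specified how to evaluate it.

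If the programmers build only what section 5 lists, the report will contain no comparison of SGA between immediate and deferred IPT, although SGA is a declared safety endpoint for in utero exposure. Someone may notice late and add the row after unblinding. The result would then look post hoc, and so would any decision to let it into the composites.

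**Working it through.** The SAP gives no figure to reproduce here. The check sets the endpoint list in section 3.2 against the outputs in section 5.

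**Step 1. Endpoint against output**

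| In utero or infant endpoint (3.2) | Output in section 5 |
|---|---|
| Fetal death | 5.10.3, both tables, as fetal demise |
| Small for gestational age | none |
| Premature birth | 5.10.3, both tables |
| Low birth weight | 5.10.3, both tables |
| Congenital anomalies | 5.10.3, first table |
| Grade 3 or higher AEs, all and related | Safety and mortality section (the second one numbered 5.10.1) |
| HIV infection | 5.10.4 |
| Hospitalization | Safety and mortality section |

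Seven of the eight have an output; SGA does not.

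**Step 2. Rows in 5.10.3**

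The first table has 6 rows and the second 4, so 6 + 4 = 10 in all. None is SGA.

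**Step 3. Could another output supply it?**

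The term appears in the SAP only in section 3.2 and in the 5.10.3 note. Section 5.10.2 summarises birth weight and gestational age at birth separately, which does not give each infant's SGA status. The infant tables of grade 3 and 4 diagnoses would show SGA only if a site happened to report it as a graded event.

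**Step 4. Could it be deferred?**

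No. Sections 1.1 and 2, quoted above, place secondary objective 1 in this report and describe the SAP as complete for it.

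**Step 5. Do the neighbouring rows replace it?**

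Not fully. On a weight-for-gestational-age definition, an infant born at 37 weeks or later and weighing 2,500 g or more can be SGA, yet appears on neither the premature-birth nor the low-birth-weight row. The SAP gives no SGA rates, so the following is an illustration on assumed inputs only. The one documented input is the target of 950 women randomized equally, that is 950 / 2 = 475 per arm. Let *b* be the share of women with a live birth (one infant per woman), *s* the SGA proportion among live births, and *f* the share of SGA infants who are term and at least 2,500 g. The number missed per arm is 475 × *b* × *s* × *f*.

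| Scenario | *b* | *s* | *f* | Live births per arm | *s* × *f* | Missed per arm |
|---|---|---|---|---|---|---|
| Low | 0.90 | 0.10 | 0.30 | 427.5 | 3.0% | 12.8 |
| Middle | 0.94 | 0.15 | 0.50 | 446.5 | 7.5% | 33.5 |
| High | 0.98 | 0.25 | 0.70 | 465.5 | 17.5% | 81.5 |

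An SGA infant with a congenital anomaly would still be counted on the anomaly row, so these figures concern only the premature-birth and low-birth-weight rows.

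**The case against.** The best defence is that this is an incomplete table list and not a contradiction. Section 3.2 declares the endpoint, the 5.10.3 note fixes its population, and section 5.10 supplies a between-arm test for its outcomes generally. Nothing says SGA will not be reported, and a careful programmer could add it. Related information is still reported by arm: birth weight, gestational age at birth, prematurity and low birth weight. The omission leaves the primary endpoint, the 5% margin, the type I error and the sample size untouched.

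Much of this is fair. It limits the consequence, and whether to call the mismatch a contradiction is a matter of wording. It does not supply the output. Section 5 is where this SAP specifies what the report contains, and the other seven endpoints in the group each have an entry there.

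Two further objections stand. The illustrative counts rest almost wholly on assumed inputs, and they ignore twins, for which section 5.10.1 on pregnancy outcomes makes provision. Also, the overlap between SGA and the neighbouring rows depends on an SGA definition that this SAP does not give. The definition may be in the protocol, so its absence here is not counted as a fault.

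**Conclusion.** The point holds. One of eight declared in utero and infant endpoints has no output, none of the 10 rows in the 5.10.3 tables is SGA, and three of the four outcomes in the live-birth note are tabulated while the fourth is not. These counts come straight from the SAP and need no assumption.

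The practical size of the gap cannot be fixed from the document. Under the assumed ranges, 3.0 to 17.5 per 100 live births (about 13 to 81 per arm) would have an SGA outcome that neither the premature-birth nor the low-birth-weight row shows. That range mostly reflects its inputs, and the finding does not depend on it.

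This should be corrected before the analysis, because a declared secondary safety endpoint would otherwise go unreported. The exclusion of SGA from the composites may be deliberate and is not itself an error.

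**What to change.** Add an SGA row to the first table in 5.10.3: number and percentage based on live births, counted per pregnancy like the other rows, with the exact mid-p comparison of section 5.10. Derive it from gestational age at birth using the source order in section 5.10.2 ("The calculation of gestational age at birth will be based on three sources"), and cite the SGA definition, from the protocol if it is given there.

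State in one sentence whether SGA counts towards the adverse pregnancy outcome composites. This needs saying because those composites are defined by the rows above them, so the position of a new row would otherwise decide the matter.

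If SGA was dropped on purpose, say so with the reason, and amend section 3.2 and the 5.10.3 note to match.

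The cost is one table row and one or two sentences. Birth weight, sex and gestational age at birth are already collected (section 5.10.2), so no new data or visits are needed.

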### **5.10.4 Summary of HIV infection status**

- Table with infant HIV infection status (positive, negative, indeterminate, unknown)

Note: To be reviewed at end of study follow-up and prior to data freezing for final analysis by selected protocol team members (pooled over study arms).

### **5.10.1 Summary of safety and mortality**

- Tables of new grade 3 and 4 labs and signs/symptoms: number (%) by SOC and grade [STATUS, PE6812, PE6817, PE6832]
- Table of new grade 3 and 4 diagnoses: number (%) by MedDRA code [EVENTS].
- Table of new grade 3 and 4 clinical and laboratory events: number (%) by MedDRA code [EVENTS]
- Listing of infant/neonatal deaths, including blinded ID, treatment arm, age at death (weeks on study), gestational age at birth, primary cause of death, narrative of etiology of death [PE1414]

- Table of infant safety summary: number (%) with any grade 3 or 4 adverse event; grade 3 or 4 adverse event definitely, probably or possibly related to study treatment based on site assessment; hospitalization; infant/neonatal death (overall, within 0-7 days of birth, within 0-28 days of birth) [EVENTS,PE9905,PE1414]

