### **1.2 Study Design (Protocol Version 2.0)**

This study is a randomized, double-blind, placebo-controlled non-inferiority trial designed to assess the overall safety and toxicity of 28 weeks of isoniazid (INH) preventive therapy (IPT) initiated during pregnancy versus deferred initiation of IPT at 12 weeks postpartum in HIV-infected pregnant women and their infants at high risk for TB infection and disease. The study will also assess the efficacy of these strategies in the women and their infants, safety and toxicity of INH *in utero* and on infants, INH resistance among *Mycobacterium tuberculosis* (*M.tb.*) isolates among participants who develop TB while on study, intensive PK of INH and ARV drugs among HIV-infected women on HAART, adherence to INH during pregnancy and postpartum, and performance characteristics of IGRA with TST among HIV-infected pregnant women and their infants.

A target of 950 HIV-infected pregnant women at  $\geq 14$  to  $\leq 34$  weeks (34 weeks, 6 days) of gestation and living in high TB incidence areas, defined as having 60 TB cases per 100,000 population in the WHO TB annual report, will be enrolled. Women who are suspected of having TB with a positive WHO TB symptom screen, have reported recent exposure to an active TB case, have received INH or TB treatment for  $>30$  days in the past year, have evidence of acute hepatitis within 90 days prior to study entry, or have  $\geq$ Grade 1 peripheral neuropathy will not be eligible.

Participants will be stratified based on gestational age at entry, and will be randomized in equal proportions to one of the following two groups:

- ARM A: Maternal INH at study entry for 28 weeks and then switched to placebo for INH until 40 weeks postpartum (immediate IPT), or
- ARM B: Maternal placebo for INH from study entry until 12 weeks postpartum and then switched to INH for 28 weeks until 40 weeks postpartum (deferred IPT)

Each maternal participant will also receive vitamin B6 and multivitamins from study entry until 40 weeks postpartum, as well as intensified TB case finding, and will be followed up to 48 weeks postpartum. Each infant participant will be followed from birth until 48 weeks postpartum with

intensified TB case finding.

The primary hypothesis is that initiation of IPT during pregnancy among HIV-infected pregnant women is as safe as deferring IPT to 12 weeks postpartum.

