### **2.3 Exploratory Objectives**

1. To evaluate population pharmacokinetics and pharmacogenomics of INH and EFV in HIV-infected pregnant and postpartum women
2. To assess the effects of INH preventive therapy on the functional characteristics of TB specific T-cell responses measured by TB ELISPOT in HIV-infected women and their infants on study
3. To evaluate adherence and exposure to INH and EFV using drug levels in hair and analyze the association between these drug levels and adverse events
4. To compare the two arms with respect to the overall (risk:benefit) clinical outcome of the mother-infant pairs
5. To explore associations of maternal and infant specific TB responses and novel biomarkers with risk of maternal and infant TB infection and disease

6. To explore the neurotoxicity of INH in combination with EFV in a subset of women

A brief description of the important study time points is shown in the following table:

Evaluations	Time points of interest
Adverse events in mothers (for primary safety analysis)	Up to week 48 postpartum
Adverse events in infants	Up to week 48 from birth
Adverse pregnancy outcomes	Delivery to week 48 from birth
Maternal TB	Up to week 48 postpartum
Infant TB	Up to week 48 from birth
Intensive and sparse PK in mothers	Antepartum (third trimester) and week 16 postpartum
TST in mothers	Delivery (or Week 4 postpartum if not done at delivery) and Week 44 postpartum
TST in infants	Week 44 from birth
IGRA in mothers	Entry, delivery and Week 44 postpartum
IGRA in infants	Week 44 from birth

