## **5.9 Primary Endpoints and Analysis**

Validation: The analysis programs in this section will be validated, and primary analysis will be double-programmed.

- Cross-tabulation of participants with at least one adverse event at least possibly related to study treatment based on IERC assessment and participants with at least one adverse event at least possibly related to study treatment based on site assessment: number (%) [TRAC]
- Table of most severe safety outcome related to study treatment among participants experiencing primary safety endpoints: number (%) of each of the following [STATUS,PE4005,TRAC]:
  - Grade 3 AE related to study treatment
  - Grade 4 AE related to study treatment
  - Death related to study treatment
  - Permanent discontinuation of study treatment due to toxicity but no grade 3 or higher AE related to study treatment
- Table of primary analysis of difference in endpoint rates between arms, based on stratified Mantel-Haenszel estimates at week 48 postpartum (primary) and simple proportions (sensitivity), for the following endpoints [STATUS,PE4005,TRAC]:
  - Primary safety endpoint
  - Any Grade  $\geq 3$  AE (all cause)
- Table of per-protocol and as-treated sensitivity analyses of difference in endpoint rates between arms, based on stratified Mantel-Haenszel estimates at week 48 postpartum and simple proportions, for the following endpoints [STATUS,PE4005,TRAC]:
  - Primary safety endpoint
  - Any Grade  $\geq 3$  AE (all cause)
- Table of sensitivity analysis coding deaths of unknown cause and all deaths as primary endpoints (if death or a prior AE experienced by the participant who died were not already considered to be a primary endpoint)
- Kaplan-Meier plot of time to endpoint from randomization date by study arm and by gestational age, with number of events and number at risk for the following endpoints
  - Primary safety endpoint
  - Any Grade  $\geq 3$  AE (all cause)
- Table of analysis of difference in endpoint rates between arms up to (i) delivery and (ii) 12 weeks postpartum, based on stratified Mantel-Haenszel estimates (primary) and simple proportions (sensitivity), for the following endpoints [STATUS,PE4005,TRAC]:

- Primary safety endpoint
- Any Grade  $\geq 3$  AE (all cause)

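### Infant Grade 3/4 events and hospitalization are summarized without an early time window, although deferred-arm mothers start INH at week 12 postpartum

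*SAP*

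**What the plan says.** Secondary objective 1 (SAP section 2.2) is "To compare safety and toxicity of INH *in utero* exposure and on infants on study". The objective therefore has two parts: exposure before birth, and infants during follow-up.

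The time-point table at the end of section 2.3 gives the window for infant adverse events as "Up to week 48 from birth". The second section numbered 5.10.1 (Summary of safety and mortality) plans a "Table of infant safety summary: number (%) with any grade 3 or 4 adverse event", followed by Grade 3/4 events related to study treatment (site assessment) and hospitalization. That section states no window for these rows, so the 48 weeks come from section 2.3. The death row alone is cut: "infant/neonatal death (overall, within 0-7 days of birth, within 0-28 days of birth". The note opening section 5.10 says exact tests will compare the arms.

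The maternal schedules in section 1.2 are:
- Immediate arm: "Maternal INH at study entry for 28 weeks and then switched to placebo for INH until 40 weeks postpartum".
- Deferred arm: "Maternal placebo for INH from study entry until 12 weeks postpartum and then switched to INH for 28 weeks until 40 weeks postpartum".

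For the mothers' primary safety endpoint and all-cause Grade 3 or higher events, section 5.9 adds a "Table of analysis of difference in endpoint rates between arms up to (i) delivery and (ii) 12 weeks postpartum". Section 5.5 does the same for hepatotoxicity. No such cut is planned for infant adverse events or hospitalization.

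**The concern.** Before week 12 postpartum only the immediate arm has had INH. From week 12 to week 40 the deferred-arm mothers take it, while immediate-arm mothers have finished or are finishing their 28 weeks. A proportion of infants with any event by week 48 combines these periods.

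If INH before birth or in the first weeks caused extra serious events soon after birth, later illness common to both arms would lower the risk ratio and widen the interval. If deferred-arm maternal INH also affected infants, it would add events to the comparison arm and shrink the difference further. An early infant signal could then go unseen, or surface only in an analysis chosen after unblinding.

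**Working it through.** **No figure to reproduce.** The SAP gives no infant event rate, effect size or power. Every risk below is an assumption.

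**Exposure arithmetic (section 1.2)**
- Follow-up after the deferred-arm switch: 48 − 12 = 36 weeks; 36/48 = 75%.
- Deferred-arm mothers on INH: 40 − 12 = 28 weeks; 28/48 = 58%.
- Immediate arm, assuming delivery at 40 weeks and entry at *g* weeks' gestation: INH weeks after delivery = 28 − (40 − *g*) = *g* − 12. Entry at 14 weeks gives 2; entry at 24 gives 12; entry at 34 weeks 6 days (34.86) gives about 22.9.
- Women entering after about 24 weeks are therefore still on INH at week 12 postpartum. At 4 weeks postpartum this applies to entry after 4 + 12 = 16 weeks, but any INH after birth within a 0-28 day window is at most 4 weeks.

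**Illustration of attenuation**

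Inputs: 475 infants per arm (target of 950 women, equal allocation, assuming one infant each); deferred-arm risk of 10% to week 12, then 10% among infants still event-free; early risk ratio 1.5; two-sided 5% test. Cumulative risk = 1 − (1 − early)(1 − late). Standard error = √{[p₁(1 − p₁) + p₀(1 − p₀)]/475}.

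- Week 12: 15.0% v 10.0%. Difference 5.0 points, SE √[(0.1275 + 0.0900)/475] = 0.0214, z = 2.3, risk ratio 1.50, power 0.64.
- Week 48, no late effect of maternal INH: 1 − 0.85 × 0.90 = 23.5% v 1 − 0.90 × 0.90 = 19.0%. Difference 4.5 points, SE √[(0.1798 + 0.1539)/475] = 0.0265, z = 1.7, risk ratio 1.24, power 0.40.
- Week 48, late risk 1.25 times higher in the deferred arm: 23.5% v 1 − 0.90 × 0.875 = 21.3%. Risk ratio 1.11, power 0.13.
- Week 48, late risk 1.5 times higher in the deferred arm: 23.5% v 1 − 0.90 × 0.85 = 23.5%. Risk ratio 1.00.

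With no late effect, and with early risk varied over 5-15% and late risk over 5-20%, the week-48 risk ratio is 1.08 to 1.37. Power is 0.36 to 0.84 at week 12 and 0.11 to 0.75 at week 48.

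**The opposite case**

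Keep the same deferred-arm risks (10% and 19%), but let a hazard ratio of 1.5 persist throughout.
- Week 12: 1 − 0.90^1.5 = 14.6% v 10.0%. SE 0.0213, z = 2.2.
- Week 48: 1 − 0.81^1.5 = 27.1% v 19.0%. SE 0.0272, z = 3.0.

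Here the 48-week count is the more sensitive one. Neither window is better for every effect shape, which argues for having both.

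**The case against.** The strongest reply is that nothing is out of line with the SAP's own endpoints. The trial compares two strategies, objective 1 includes "exposure and on infants on study", and section 3.2 lists infant events and hospitalization with no early window. The maternal cuts exist because objective 3 names pregnancy and the immediate postpartum period; objective 1 names no such period. All of this stands: the 48-week table is a proper analysis and the maternal parallel does not prove an omission.

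A reader might infer that the whole in utero comparison is diluted. The SAP does not support that. Fetal demise, prematurity, low birth weight and congenital anomalies (section 5.10.3) are essentially settled by delivery and cannot be diluted by INH started at week 12, and deaths already have 0-7 and 0-28 day cuts. Only the Grade 3/4 and hospitalization rows are left without an early view.

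A reader might also take birth to week 12 as isolating in utero exposure. It does not, because many immediate-arm mothers may still be taking INH after delivery.

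Nor can the week-48 contrast be called reversed. That needs infant exposure through breast milk, and the SAP says nothing about breastfeeding. Attenuation by background events does not depend on it.

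Finally, the loss of power is assumed, and a persistent effect is detected better at week 48. That limits the claim to a possible loss, not a demonstrated one.

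**Conclusion.** The point holds as a gap in presentation, not as an error in the 48-week table. As written, the infant summary cannot show whether Grade 3/4 events or hospitalizations differ between arms before deferred-arm INH begins, and 75% of the follow-up it covers comes after that.

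The size is hypothetical. If an effect were confined to the first 12 weeks, a risk ratio of 1.5 would appear as 1.08 to 1.37 at week 48 over the assumed risks, from background events alone, and could vanish if late maternal INH also affected infants. If the effect persisted or began after week 12, there would be no such dilution. The conclusion rests on the INH schedules and the 48-week window, both stated in the SAP; the event risks, the one-infant-per-woman count and delivery at 40 weeks are assumptions.

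This is a cheap improvement worth making before unblinding.

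**What to change.** In the infant safety summary:
- Keep the 48-week column as the comparison of strategies, and state that window in the section.
- Add 0-28 days and birth to week 12 for Grade 3/4 events (all-cause and related) and for hospitalization.
- Add birth to week 12 for death, which already has the 0-28 day cut.
- Label birth to week 12 as the period before deferred-arm INH starts, not as isolating in utero exposure. Note that 0-28 days comes closer to that.
- Report the between-arm difference with a confidence interval in each window, and mark the early windows as supportive.

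The cut-points are already used elsewhere in the SAP: 0-28 days for infant death and week 12 for maternal safety. The cost is a few columns in one table plus a sentence of text, provided onset dates are recorded for these events; the SAP does not say so for hospitalization, and this should be confirmed. The downside is more comparisons, with fewer events in each early window.
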